7.2.4.2. Laboratory Data

For the purposes of summarization in both the tables and listings, all laboratory values will be converted to standardized units. If a laboratory value is reported using a non-numeric qualifier (e.g., less than [$<$] a certain value, or greater than [$>$] a certain value), the given numeric value will be used in the summary statistics, ignoring the non-numeric qualifier.

By-patient listings to be presented include hematology, serum chemistry, urinalysis, and tumor marker for HCC AFP. Laboratory test results (units), normal range (H and L), with change from baseline (baseline value will be flagged in the listing), and CTCAE grades if applicable will be presented in laboratory listings. Patients who developed toxicities of Grade ≥ 3 will be flagged in the listings. The parameters to be listed are as follows:

- Hematology: hemoglobin, hematocrit, red blood cell (RBC), white blood cell (WBC), platelets, neutrophils, lymphocytes, monocytes, eosinophils, basophils, prothrombin time, and International Normalized Ratio (INR)
- Chemistry: sodium, potassium, chloride, carbon dioxide (CO₂), glucose, magnesium, calcium, phosphorus, total and direct bilirubin, alanine aminotransferase (ALT), aspartate aminotransferase (AST), serum creatinine, lactate dehydrogenase (LDH), total protein, albumin, alkaline phosphatase (ALP), blood urea nitrogen (BUN), and uric acid.
- Urinalysis: specific gravity, protein, glucose, urinary sodium, urinary phosphate, and urinary creatinine.
- Tumor markers: AFP, AFP-L3%, des-gamma-carboxy prothrombin (DCP), CA242

Shift tables will be constructed for toxicity gradable laboratory parameters to tabulate changes in NCI CTCAE for toxicity (version 4.0) from baseline to post baseline worst CTCAE grade for gradable laboratory tests. Unscheduled laboratory test results will be included in laboratory shift tables.

For all lab parameters collected in the CRF, summary statistics for baseline values and maximum change from baseline will be presented by phase, treatment arm and dose level cohort based on the safety analysis set. Figures of maximum post-baseline vs baseline values will be plotted along with E-DISH scatter plots for key lab parameters, including but not limited to neutrophils, platelets, and liver function tests (ALT, AST, ALP, and total bilirubin).

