## 4.7 **Dose-Limiting Toxicity**

Dose-Limiting Toxicity (DLT) is defined as the occurrence of any of the following toxicities possibly, probably, or definitely related to study drug (either BBI608 or BBI503) or to study drug in combination with sorafenib during the first 28 days of combination therapy, unless there is a clear alternative explanation:

- CTCAE (Common Terminology Criteria for Adverse Events) Grade 4 hematological toxicity.
- Grade 3 thrombocytopenia in the presence of active bleeding.
- Grade 3 or 4 non-hematological toxicity, except for Grade 3 nausea/vomiting/anorexia, diarrhea, or fatigue, symptoms that will be considered DLTs only if they persist more than seven (7) days despite optimal medical management. Grade 4 toxicity will be considered DLT.

Alopecia will not be considered a DLT. Assessment of DLTs will occur during the first 28 days of BBI608 or BBI503 therapy in combination with sorafenib. DLTs will be determined from both adverse events and changes from baseline in physical examination findings and laboratory parameters.

\* Once the amendment 3 is in effect, Arm 2 in the Phase II portion will be closed for enrollment.

The criteria for determination of DLTs will apply to a given administration schedule independently. Patients who discontinue protocol therapy for a reason other than a DLT may be replaced in order to fully evaluate a given dose-level.

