#### 7.7 Concomitant Medication

#### **7.7.1** Permitted Treatment

All information regarding concomitant treatments (medications or procedures) must be recorded on the patient's CRF (including the name of the medication or procedure and duration of treatment).

Palliative and supportive care for disease-related symptoms will be offered to all patients in this study. Patients may receive palliative radiation therapy.

In addition, the following treatments are allowed:

- Standard therapies for concurrent medical conditions
- Epoetin alfa (Epogen®, Procrit®)
- Hematopoietic growth factors, including filgrastim (Neupogen®) Thrombopoietin (e.g., Romiplostim (Nplate®), or other granulocyte colony stimulating factors (G-CSF), are permitted Prophylactic anti-emetics and/or anti-diarrheal agents may be administered according to standard practice
- Megestrol acetate (Megace®)
- Dexamethasone
- Diphenhydramine
- Cimetidine
- Ranitidine
- Bisphosphonates
- Denosumab

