7.2.4.4. Vital Signs

For weight, temperature, heart rate, respiration rate, systolic blood pressure (SBP), and diastolic blood pressure (DBP), summary statistics for baseline values and maximum change (maximum increase, maximum decrease and no change) from baseline will be summarized based on the safety analysis set. A patient listing will also be provided.

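### The SAP's laboratory figures plot the highest post-baseline neutrophil and platelet count, so they cannot show the nadir and they understate cytopenia

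*SAP*

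**What the plan says.** SAP section 7.2.4.2 (Laboratory Data) specifies one plotted statistic for its key laboratory figures: "Figures of maximum post-baseline vs baseline values will be plotted along with E-DISH scatter plots for key lab parameters". It then names the parameters, "including but not limited to neutrophils, platelets, and liver function tests (ALT, AST, ALP, and total bilirubin". No minimum or worst-direction figure is specified for any test.

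The sentence before it covers the numerical table for every laboratory parameter on the CRF: "summary statistics for baseline values and maximum change from baseline will be presented", split by phase, arm and dose cohort. It does not say whether the change is a rise, a fall or the larger of the two.

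The same section also plans shift tables from baseline to the worst post-baseline CTCAE grade, with unscheduled results included. By-patient listings will show each result, its change from baseline and its grade, with Grade 3 or higher flagged.

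SAP section 7.2.4.4 (Vital Signs) does state the direction: "maximum change (maximum increase, maximum decrease and no change) from baseline".

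On which direction is harmful, Protocol section 4.7 counts "Grade 3 thrombocytopenia in the presence of active bleeding" as a dose-limiting toxicity, along with "CTCAE (Common Terminology Criteria for Adverse Events) Grade 4 hematological toxicity".

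**The concern.** One rule is applied to tests whose harm runs in opposite directions. For ALT, AST, ALP and bilirubin the maximum is the value of interest. For neutrophils and platelets it is the value furthest from the toxicity of interest.

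Tolerability and safety come first in the phase II primary objective (Protocol section 2.1), and patients may enter with platelets as low as 60 x 10^9/L (Protocol section 3.1, criterion 17). Protocol section 10.6 promises descriptive statistics of laboratory changes over time, but SAP section 7.2.4.2 contains no by-visit summary. The figures and the table of maximum change are therefore the aggregate displays of laboratory values on their own scale, since the shift tables work by grade. A reader who goes to the platelet figure to see how far counts fell from baseline will see the highest count each patient reached after baseline.

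**Working it through.** The question is which order statistic is plotted. The documents give no figure to reproduce, so the check compares passages and adds an illustration with assumed values.

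**Step 1. Do the counts belong to the maximum-versus-baseline figures?** The sentence names two kinds of display, the maximum-versus-baseline figures and E-DISH plots. E-DISH is by convention a liver-safety plot. Neutrophils and platelets can therefore only refer to the first kind.

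**Step 2. Could *maximum* be shorthand for *worst*?** The SAP uses *worst* when it means worst: for CTCAE grade in the shift tables of section 7.2.4.2, and for the ECG shift tables in section 7.2.4.3. Where both directions matter, section 7.2.4.4 names both. A programmer following the text would take the maximum.

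**Step 3. When does the choice matter?** It matters whenever a patient has at least two differing post-baseline counts, because the minimum is then below the maximum and cannot be the plotted value. Haematology is scheduled on Cycle 1 Day 15, on Day 1 of each later cycle and at the end-of-study visit (Protocol sections 5.4.3, 5.5.1, 5.6.1 and 5.8), so repeated values are expected. This shows how often the nadir is not the plotted value. It does not show how often the difference is large.

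**Step 4. Illustration (assumed platelet counts, x 10^9/L, baseline 100).**

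| Post-baseline values | Planned point (baseline, maximum) | Alternative point (baseline, minimum) |
|---|---|---|
| 85, 25, 110 | (100, 110): 110 − 100 = a rise of 10 | (100, 25): 100 − 25 = a fall of 75 |
| 85, 25 | (100, 85): 100 − 85 = a fall of 15 | (100, 25): 100 − 25 = a fall of 75 |

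In the first row the count rebounds above baseline, and the planned point lies above the line of identity, suggesting improvement. In the second row there is no rebound. The planned point lies below the line but shows a fall of 15 where the largest fall was 75. The figure understates the fall in both rows and reverses it only in the first.

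**Step 5. Can a high value reflect something other than good tolerability?** Yes. Protocol section 7.7.1 permits "Hematopoietic growth factors, including filgrastim", so a patient's highest count may be a rebound after support.

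**Step 6. The numerical summary.** For the first row, maximum change read as the largest increase gives +10 and misses the fall. Read as the largest absolute change it gives −75 for this patient, but across patients it would mix rises and falls in one statistic. Reporting both directions gives +10 and −75. The first reading would miss falls in haemoglobin and albumin as well as in the counts.

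**The case against.** The strongest reply is that the nadir is not lost from the report. The worst-grade shift tables include unscheduled results. The listings give every value with its change from baseline and flag Grade 3 or higher. Cytopenias reported as adverse events are tabulated by maximum grade, with a separate table for Grade 3 or higher, and gastrointestinal haemorrhage has its own table (SAP section 7.2.4.1). All of this stands. It limits the point to the figures, where the depth of the fall on the continuous scale is missing. It does not make the plotted statistic right for counts.

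A second reply is that no decision rests on these figures. This also stands. DLTs are determined from adverse events and from changes in examination and laboratory findings during the first 28 days of combination therapy (Protocol section 4.7). Escalation uses the number of patients with a DLT (SAP section 3.2.1), and there is no hypothesis testing (SAP section 3.1). A reader might infer from the DLT criteria for haematological toxicity that dose finding is compromised; the documents do not support that.

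Third, a reader might infer that the figure shows the opposite of the truth for nearly every patient. That goes too far. It reverses the picture only when some post-baseline count exceeds baseline, and the documents give no information on how often that would happen.

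Fourth, maximum change is ambiguous in the laboratory table; it is not specified in the wrong direction. That is correct, and the request there is only for a definition.

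**Conclusion.** The point holds for the descriptive laboratory figures. Followed as written, SAP section 7.2.4.2 produces neutrophil and platelet plots that show the highest post-baseline value, cannot show the nadir when counts differ, understate cytopenia, and can suggest improvement after a rebound. The undefined maximum change in the table is a related, weaker problem that needs a definition.

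The size is modest. A reader might conclude that the SAP conceals cytopenia. It does not: low counts are still captured by grade in the shift tables and by value in the listings. DLT assessment and the response endpoints are untouched. The change is still worth making, because these are the plots chosen for key parameters and safety is part of the phase II primary objective.

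The conclusion rests on reading *maximum* literally, which the SAP's wording elsewhere supports, and on a fall being the toxicity of interest for both counts. The protocol states this for platelets through thrombocytopenia; for neutrophils it is the ordinary clinical reading. The platelet values in the illustration are assumed. The number of patients materially affected cannot be derived from the documents.

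**What to change.** In SAP section 7.2.4.2:

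- Plot minimum post-baseline against baseline for neutrophils and platelets, and for any other plotted test where a low value is harmful, such as haemoglobin or albumin.
- Keep maximum post-baseline against baseline for ALT, AST, ALP and total bilirubin, and leave the E-DISH plots as they are.
- In the numerical summary, replace maximum change with maximum increase and maximum decrease from baseline, matching section 7.2.4.4.

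If *worst* was intended all along, this only makes the intention explicit. The cost is a short wording change, a minimum in place of a maximum in the figure programs for the counts, and one added statistic in the table. No new data are needed and no other analysis changes.

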7.2.4.3. Electrocardiograms

12-lead electrocardiogram (ECG) with categorical results (Normal, Abnormal [Not clinically significant], Abnormal [Clinically significant]) will be summarized. Shift tables showing results from baseline to worst post baseline will be provided. A patient listing will also be provided.

7.2.4.4. Vital Signs

For weight, temperature, heart rate, respiration rate, systolic blood pressure (SBP), and diastolic blood pressure (DBP), summary statistics for baseline values and maximum change (maximum increase, maximum decrease and no change) from baseline will be summarized based on the safety analysis set. A patient listing will also be provided.

7.2.4.5. Physical Exams

Physical examination findings (Normal, Abnormal, or Not Done) will be collected per protocol schedule. Data will be presented in a by-patient listing.

9. APPENDICES

Appendix 1.1. Response Criteria by RECIST 1.1

	Evaluation of target lesions
Complete Response (CR):	Disappearance of all target lesions Any pathological lymph nodes must have reduction in short axis of <10mm
Partial Response (PR):	At least a 30% decrease in the sum of the longest diameter (LD) of target lesions, taking as reference the baseline sum LD
Progressive Disease (PD):	At least a 20% increase in the sum of the LD of target lesions, taking as reference the smallest sum LD recorded since the treatment started. In addition to the increase of 20%, the sum must also demonstrate an absolute increase of at least 5mm. The appearance of one or more new lesions is also considered progression.
Stable Disease (SD):	Neither sufficient shrinkage to qualify for PR nor sufficient increase to qualify for PD, taking as reference the smallest sum LD since the treatment started

	Evaluation of non-target lesions
Complete Response (CR):	Disappearance of all non-target lesions and normalization of tumor marker level. All lymph nodes must be non-pathological in size (<10mm short axis)
Stable Disease (SD):	Persistence of one or more non-target lesion(s) and/or maintenance of tumor marker level above normal limits
Progressive Disease (PD):	Appearance of one or more new lesions and/or unequivocal progression of existing non-target lesions

Appendix 1.2. Response Criteria by mRECIST 1.1

	Evaluation of target lesions
Complete Response (CR):	Disappearance of any intratumoral arterial enhancement in all target lesions
Partial Response (PR):	At least a 30% decrease in the sum of diameters of viable (enhancement in the arterial phase) target lesions, taking as reference the baseline sum of the diameters of target lesions
Progressive Disease (PD):	An increase of at least 20% in the sum of the diameters of viable (enhancing) target lesions, taking as reference the smallest sum of the diameters of viable (enhancing) target lesions recorded since treatment started
Stable Disease (SD):	Any cases that do not qualify for either partial response or progressive disease

	Evaluation of non-target lesions
Complete Response (CR):	Disappearance of intratumoral arterial enhancement
Stable Disease (SD):	Persistence of intratumoral arterial enhancement in one or more non-target lesions
Progressive Disease (PD):	Appearance of one or more new lesions and/or unequivocal progression of existing non-target lesions

Patients with an imaging assessment that meets criteria for either complete response (CR) or partial response (PR) according to RECIST 1.1 or mRECIST should have a repeat, confirmatory, radiologic assessment approximately 4 weeks after the assessment in which CR or PR criteria were met.

Appendix 1.3. Evaluation of Best Overall Response

Target lesions	Non-Target lesions	Evaluation of New lesions	Overall response
CR	CR	No	CR
CR	Non-CR/non-PD	No	PR
CR	Not evaluated	No	PR
PR	Non-PD or not all evaluated	No	PR
SD	Non-PD or not all evaluated	No	SD
PD	Any	Yes or No	PD
Any	PD	Yes or No	PD
Any	Any	Yes	PD

The best overall response (BOR) is the best response recorded from start date until disease progression or start of new anti-cancer therapy. BOR is determined by the following order:

CR: One objective status of CR documented before progression or start of new anti-cancer therapy.

PR: One objective status of PR documented before progression and start of new anti-cancer therapy, but not qualifying as CR.

SD: At least one objective status of SD documented at least (8 weeks – 7 days) after start date and before progression and the start of new anti-cancer therapy but not qualifying as CR or PR.

PD: Progression documented within (16 weeks + 7 days) after start date and not qualifying as uCR, uPR, or SD.

NE: All other cases. Note that reasons for NE should be summarized and the following reasons could be used:

- Early death (Note: death prior to (8 weeks – 7 days) after start date)
- No post-baseline assessments
- All post-baseline assessments have overall response NE
- New anti-cancer therapy started before first post-baseline assessment
- SD too early (< (8 weeks – 7 days) after start date))
- PD too late (> (16 weeks + 7 days) after start date)

Special and rare cases where BOR is NE due to both early SD and late PD will be classified as ‘SD too early’.

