#### **5.7.2** Per-Protocol

Per-protocol radiologic assessments will be performed every eight weeks (56 days), as calculated according to the date of the first dose of the sorafenib run-in period. A window of ±7 days is allowed when scheduling radiologic disease assessments (applies to each scan individually). Per-protocol radiologic assessments are defined as a computed tomography (CT) with intravenous contrast of the chest, abdomen, and pelvis with tri-phasic liver scan. For those with an allergic reaction to intravenous CT contrast despite appropriate pre-treatment measures, per-protocol evaluation with magnetic resonance imaging (MRI) of the abdomen and pelvis with gadolinium plus a non-contrast CT scan of the chest is required.

Additional radiologic evaluations when clinically indicated are allowed. However, evaluations obtained for clinical indications cannot be substituted for per-protocol radiologic assessments unless they also satisfy the above per-protocol definition of radiologic assessment.

Per-Protocol radiologic evaluations should be performed every 8 weeks (56 days) until radiologic disease progression is observed according to *both* RECIST 1.1 and modified RECIST for patients with HCC. If protocol therapy is permanently discontinued for any reason without documentation of PD per RECIST 1.1 and mRECIST for HCC, per-protocol imaging evaluations should continue every 8-weeks until criteria for disease progression are satisfied according to both RECIST 1.1 and mRECIST for HCC.

Patients with an imaging assessment which meets criteria for either complete response (CR) or partial response (PR) according to RECIST 1.1 or mRECIST should have a repeat, confirmatory, radiologic assessment approximately 4 weeks after the assessment in which CR or PR criteria were met. After the confirmatory image, radiologic assessments return to the every 8 week schedule.

If, at any time, a determination is made for a study subject to discontinue protocol therapy, the treating investigator should determine the likelihood that the patient will be able to attend the next scheduled radiologic assessment. If the treating investigator feels it is unlikely that a patient will be able to obtain the next scheduled per-protocol radiologic assessment, a per-protocol radiologic assessment should be obtained as soon as possible (a minimum of 4 weeks, however, should elapse between per-protocol assessments).

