2. ENDPOINTS AND COVARIATES: DEFINITIONS AND CONVENTIONS

2.1. Primary Endpoint(s)

Phase Ib

- Dose-Limiting Toxicities (DLTs): For definition of DLT, see section 3.10 of the Protocol [1].

Phase II

- Objective Response Rate (ORR) and Disease Control Rate (DCR).

ORR is defined as the percentage of patients with a best overall response (BOR) of complete response (CR) or partial response (PR), using both RECIST and mRECIST assessment data.

DCR is defined as the percentage of patients with a best overall response (BOR) of complete response (CR) or partial response (PR) or stable disease (SD), using both RECIST and mRECIST assessment data. Response Criteria by RECIST and mRECIST is provided in Appendix 1.1 and 1.2, respectively. The categorizations of response (CR, PR, SD, progressive disease [PD], and not evaluable [NE]) and the derivations of BOR are provided in Appendix 1.3.

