7.2.2. Analysis for Primary Endpoint

7.2.2.1. Dose-Limiting Toxicity (Phase Ib)

7.2.2.2. Dose-Limiting Toxicity is the primary endpoint of the dose escalation component of the study, which will be summarized by treatment groups using the safety analysis set for patients in the dose escalation portion of the study. A listing of the DLTs will be provided. Objective Response Rate and Disease Control Rate

The ORR is defined as the percentage of patients with a BOR of CR or PR, and the DCR is defined as the percentage of patients with a BOR of CR or PR or SD. The categorizations of response (CR, PR, SD, PD, and NE) and the derivations of BOR are provided in Appendix 1.3.

ORR/DCR will be summarized for the ITT analysis set and repeated for the response evaluable analysis set as sensitivity analysis. ORR/DCR point estimates for each treatment arm will be provided along with the corresponding 2-sided 95% confidence intervals using an exact method [3].

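### The SAP awards CR or PR on a single scan, so the phase II ORR can count responses that the planned confirmatory scan did not bear out, and no planned analysis shows how many

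*SAP*

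**What the plan says.** **The confirmatory scan.** Protocol 5.7.2 covers patients whose imaging shows CR or PR by either criterion, mRECIST or RECIST 1.1, and says that they "should have a repeat, confirmatory, radiologic assessment approximately 4 weeks after the assessment in which CR or PR criteria were met". Imaging then goes back to the 8-week schedule. SAP Appendix 1.2 repeats the instruction. Neither text says what the result does to the response classification.

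**The response rule.** SAP Appendix 1.3 assigns best overall response (BOR) in order. For partial response the line reads "PR: One objective status of PR documented before progression and start of new anti-cancer therapy, but not qualifying as CR". The line for complete response works the same way: a single scan with that status is enough.

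The PD category in the same list covers early progression "not qualifying as uCR, uPR, or SD". The labels uCR and uPR appear nowhere else in either document.

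**The endpoint.** SAP 2.1 names ORR and DCR as the phase II primary endpoints, by both criteria. SAP 7.2.2 builds ORR directly on BOR: "The ORR is defined as the percentage of patients with a BOR of CR or PR". ORR is reported in the ITT set with an exact 95% interval and repeated in the response evaluable set as a sensitivity analysis.

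**The protocol's own definitions.** Protocol 10.4.2 defines ORR as the proportion with a documented CR or PR. Sections 9.1.5 and 9.2.4 take BOR from all overall responses up to progression. None of these asks for confirmation.

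**The concern.** Both documents schedule an extra scan whose stated purpose is to confirm a response. The rule that produces ORR gives that scan no power to do so.

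The effect runs one way. Because BOR takes the best status, the extra scan can raise a PR to a CR. A scan prompted by an mRECIST response can even add a RECIST 1.1 response. It cannot remove a response.

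Three features of the trial make this worth settling:
- Site staff collect the lesion measurements (Protocol 5.7.4) and are not blinded (Protocol 7.5).
- mRECIST follows at most two target lesions, measured by viable enhancing diameter (Protocol 9.2.1), so one borderline measurement can decide a PR.
- There is no hypothesis test (SAP 3.1), so the ORR estimate and its interval are the result, and their meaning depends on what counts as a response.

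The only planned sensitivity analysis of ORR changes the population and leaves the response rule as it is. The undefined uCR and uPR add doubt, because a programmer cannot tell whether single-scan responses were meant to be CR and PR or a separate class.

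**Working it through.** The documents give no expected ORR and no rate of non-confirmation, so there is no planned figure to reproduce. The check has two parts.

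**1. Apply the rules to example scan sequences.** Days run from the start date. The SD minimum in Appendix 1.3 is 8 weeks - 7 days = 56 - 7 = day 49. The limit for PD is 16 weeks + 7 days = 112 + 7 = day 119. The right-hand column assumes that a second CR/PR is needed at least 28 days later with no PD in between. It also assumes that an unconfirmed CR/PR at day 49 or later counts as SD.

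| Scans | BOR by Appendix 1.3 | BOR if confirmation is needed |
|---|---|---|
| PR day 56, PR day 84 | PR | PR |
| PR day 56, SD day 84 | PR | SD |
| PR day 56, PD day 84 | PR | SD |
| CR day 56, PD day 84 | CR | SD |
| PR day 56, no further scan | PR | SD |
| PR day 40 (off schedule), PD day 68 | PR | PD |

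In rows 2 to 4 and in the last row the later scan did not bear out the response, yet the patient stays a responder, because the response was recorded before progression. Row 5 is a different case: the response was never checked.

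DCR is largely unaffected, since rows 2 to 5 move only from response to SD. The last row shows the exception: a response before day 49 can fall out of disease control altogether.

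**2. Size the effect on ORR.** The target is 30 patients in Arm 1 and 30 in Arm 3 (Protocol 10.3). Each unconfirmed response is worth 1/30 = 3.3 percentage points. In Arm 2, closed at about 10 patients, it is worth 1/10 = 10 points.

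Exact (Clopper-Pearson) 95% intervals for n = 30, with responder counts assumed for illustration only:

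| Responders | ORR | 95% CI |
|---|---|---|
| 1/30 | 3.3% | 0.1 to 17.2 |
| 2/30 | 6.7% | 0.8 to 22.1 |
| 3/30 | 10.0% | 2.1 to 26.5 |
| 4/30 | 13.3% | 3.8 to 30.7 |
| 6/30 | 20.0% | 7.7 to 38.6 |

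If two of six single-scan responders are not confirmed, ORR falls from 20.0% to 13.3%. If two of four are not, it falls from 13.3% to 6.7%. In both cases the intervals overlap widely.

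**The case against.** The strongest reply is that the SAP does what the protocol says. The protocol's ORR and BOR definitions set no confirmation condition, and the scan instruction in 5.7.2 is a recommendation within the imaging schedule. A reader might infer that the SAP departs from a protocol rule of confirmed response; the documents do not support that.

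Other points on this side also stand:
- The extra scan is not wasted. A PD on it feeds PFS, and a CR on it upgrades BOR. The listings in SAP 7.2.3.2 include the first and last dates with CR or PR, so single-scan responses could often be picked out by hand.
- Only the SAP calls ORR primary. Protocol 10.4.2 places it under secondary objectives, although preliminary anti-tumor activity is part of the phase II primary objective. The efficacy proportion named in Protocol 10.5 is PFS-4.
- The same rule applies in the sorafenib-alone arm, and no decision in the documents depends on ORR crossing a threshold.
- The same unblinded staff would read the second scan, so confirmation does not remove reader bias.
- If u means unconfirmed, the PD line can be read as consistent with a deliberate single-scan rule.

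These points remove any charge of breach and weaken the case for making confirmed response the only definition. They do not supply an ORR whose confirmation status is stated, or a summary of how many responses held up. The last point is itself a guess about an undefined label.

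**Conclusion.** The point holds as a gap in the definition and reporting of ORR. As written, the rule lets a response count when the planned confirmatory scan does not bear it out, and nothing planned qualifies ORR for this. Each such patient moves ORR by 3.3 percentage points in an arm of 30.

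A reader might go further and conclude that the reported ORR does contain refuted responses, or that it is doubled. The documents hold no response data, and a doubling appears only if half of the assumed responders fail confirmation. With no hypothesis test, there is also no effect on type I error or power.

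The conclusion rests on reading Appendix 1.3 literally, with uCR and uPR having no force of their own, and on the target of 30 per open arm.

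**What to change.** In SAP Appendix 1.3:

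1. Define confirmed CR/PR as a second CR/PR at the confirmatory scan or later, with no PD in between, separately for RECIST 1.1 and mRECIST. Match the interval to the protocol's scan window. A strict 28-day minimum would reject a scan done on day 26, which still fits the protocol's approximate timing. Protocol 5.7.2 allows 7 days either side for scheduled scans, and the SAP should say whether that applies here.
2. In the confirmed analysis, class an unconfirmed CR/PR as SD if it falls at least (8 weeks - 7 days) after the start date. The SD line must say that a CR or PR status meets the SD minimum, since it now asks for a recorded SD. Earlier responses fall to PD or NE under the existing rules.
3. Report confirmed and unconfirmed ORR side by side per arm, each labelled, with exact 95% intervals. Add the number of responders who had no confirmatory scan, so that refuted and unchecked responses can be told apart.
4. State which of the two is primary.
5. Define or replace uCR and uPR.

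The cost is SAP wording and one more derivation; the scans are already in the schedule. Confirmed ORR may be lower, and a responder who misses the confirmatory scan counts as a non-responder in that row. The unconfirmed row and the count in item 3 keep those patients visible.
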